#### 4.6.3. Additional Safety Assessments

#### 4.6.3.1. Laboratory Parameters

Laboratory assessments are defined in the Protocol Section 10.3.

Clinical safety laboratory parameters will be expressed in standard international units. Laboratory data collected and recorded below lower limit of quantification (LLOQ) will be set to LLOQ for calculation of summary statistics (eg, < 400 U/L will be imputed as 400). Summaries will only include data analyzed from a central laboratory.

Summaries for each laboratory parameter (hematology, chemistry, coagulation, and urinalysis), which are continuous variables, will have a tabular summary of descriptive statistics at each scheduled visit. Descriptive statistics include actual value and change from Baseline at each scheduled visit.

Shift tables will be generated to summarize shifts from baseline categories to the worst postbaseline categories with directionality specified for any laboratory values, which could be reported in either direction (eg, above ULN or below ULN). Clinical laboratory tests with normal ranges will be classified as low, normal, and high. For these tests, abnormal values will be flagged in the listings with H when the value is higher than the upper limit of the reference ranges and with L when the value is lower than the lower limit of the reference ranges.

For hematology and chemistry laboratory values, summary tables of potentially clinically significant abnormalities will also be provided.

Separate listings of laboratory data collected from central compared and local laboratories will be generated. Out-of-range laboratory results will be identified in listings.

Boxplots will be presented over time by scheduled visit for planned chemistry and hematology parameters.

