 - b. Electromyography evidence of active myositis within the last 6 months prior to or during Screening
 - c. Magnetic resonance imaging (MRI) muscle evidence of active myositis within the last 6 months prior to or during Screening
 - d. At least 1 muscle enzyme (CK, LDH, aldolase, AST, ALT) in the IMACS panel ≥ 2 times ULN at Screening
 - e. Active DM skin rash characterized by inflammatory changes (CDASI Activity Score ≥ 7) at Screening
- 9. Vaccinated against *N meningitidis* within 3 years prior to initiating ravulizumab as per national and local guidelines. Participants must receive the vaccination at least 2 weeks before first study intervention. The sponsor recommends that national and local guidelines for prophylactic antibiotics should also be followed.
- 10. Participants who have been diagnosed with cancer within the last 3 years need to have appropriate negative cancer screening as per local standard of care within 6 months before Screening (basal or squamous cell skin cancer or carcinoma in situ of the cervix needs to have been excised and without evidence of residual disease for at least 3 months before Screening).

Pregnancy and Contraception

11. Female participants of childbearing potential and male participants must follow specified contraception guidance as described in the protocol.

Informed Consent

12. Capable of giving signed informed consent as described in the protocol, which includes compliance with the requirements and restrictions listed in the Informed Consent Form (ICF) and the protocol.

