activity	decrease, or negative percentage	> 5% to 15% improvement	2.5
(enzyme	change, in the enzyme with the most	> 15% to 25% improvement	5
specific d)	abnormal activity level	> 25% to 40% improvement	7.5
		> 40% improvement	7.5
Extramuscular	"Improvement" is defined as a	Worsening to 5% improvement	0
disease activity	decrease, or negative percentage	> 5% to 15% improvement	7.5
(0.0-10.0 cm)	change, in extramuscular disease	> 15% to 25% improvement	12.5
	activity score	> 25% to 40% improvement	15
		> 40% Improvement	20

Table 3:IMACS-TIS Algorithm

- a Absolute percentage change is calculated as follows:  $100 \times \left(\frac{\text{Follow-up value baseline value}}{\text{Parts}}\right)$
- b The muscle enzyme that has the most abnormal serum activity is defined as the enzyme with the highest Baseline level as a percentage of the ULN for the relevant enzyme.
- c The most abnormal muscle enzyme will be selected from the following at Baseline and followed over time: creatine kinase; aldolase; alanine aminotransferase; aspartate aminotransferase; and lactate dehydrogenase.
- d The range for each enzyme will be defined based on a multiple of the ULN for that enzyme as follows: creatinine kinase range =  $15 \times ULN$ ; aldolase range =  $6 \times ULN$ ; alanine aminotransferase, aspartate aminotransferase, and lactate ranges =  $3 \times ULN$ .
- Abbreviation: CSM = core set measure; HAQ = Health Assessment Questionnaire; IMACS-TIS = International Myositis Assessment and Clinical Group - Total Improvement Score; MMT = manual muscle testing; ULN = upper limit of normal

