For each of the 5 CSMs, the outcome variable is change from Baseline in CSM at Weeks 2, 10, 18, and 26 and will include fixed effects of treatment arm (ravulizumab, placebo), visits (Weeks 2, 10, 18, and 26), treatment by visit interaction term, and adjustment for baseline of the core set measure. An unstructured covariance matrix will be used to model the correlations among repeated measurements within each participant. The Kenward-Roger approximation will be used to calculate the denominator degrees of freedom. If the model using the unstructured correlation matrix fails to converge, then an alternative correlation structure resulting in best model fit based on the QIC criterion (ie, smallest QIC) will be used among the following correlation structures: autoregressive (1), Toeplitz, and exchangeable.

Within each CSM, the LS mean with corresponding standard error and 80% CIs will be displayed by treatment arm and visit. The LS mean treatment difference (ravulizumab - placebo) in the CSM at Week 26 will be presented along with the 80% CI along with the corresponding p-value.

In addition, change from Baseline in each of the muscle enzymes (sixth CSMs) will be analyzed using the MMRM model as specified above. A separate model for each muscle enzyme (creatine

kinase, aldolase, alanine aminotransferase, aspartate aminotransferase, and lactate dehydrogenase) will be generated.

Descriptive statistics of actual and change from Baseline in the 5 CSM will also be generated by treatment arm at each scheduled visit.

#### 4.3.4. Response Related to Muscle Enzymes - Normalization of Most Abnormal Baseline Enzyme at Week 26

Muscle enzymes are classified as the following 5 laboratory parameters: creatine kinase, aldolase, alanine aminotransferase, aspartate aminotransferase, and lactate dehydrogenase. For each participant, at Baseline, the most abnormal muscle enzyme is the laboratory parameter with the highest ratio (result/ULN) among the 5 laboratory parameters. Normalization of the most abnormal Baseline enzyme will be achieved if the result is less than the ULN (eg, ratio  $\leq 1$ ).

Participants will be defined as a responder at Week 26 if:

- 1. The participant achieves normalization of the most abnormal baseline muscle enzyme (eg, ratio  $\leq$  1) at Week 26 and
- 2. The participant did not have a relevant IE (defined in Section 4.2 and Table 2) up to and including Week 26 and
- 3. The participant did not have normal muscle enzymes at Baseline.

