## 6.5. Potentially Clinically Significant Criteria

Parameter	PCSA Low	PCSA High
Chemistry		
Potassium	< 3 mmol/L	$\geq$ 6 mmol/L
Calcium	< 1.75 mmol/L	> 3.4 mmol/L
Sodium	$\leq$ 129 mmol/L	$\geq$ 155 mEq/L
Blood urea nitrogen		> 40  mg/dL
Creatinine		> 186 umol/L
Total bilirubin		$> 2 \times ULN$
Alkaline phosphatase		$> 3 \times ULN$
AST		$> 3 \times ULN$
ALT		$> 3 \times ULN$
Albumin	$\leq$ 30 g/L	
Chloride	< 80 mmol/L	> 130 mmol/L
Glucose	< 3 mmol/L	
Hematology		
Hemoglobin	$\leq$ 115 g/L (male) $\leq$ 95 g/L (female)	$ \geq 185 \text{ g/L (male)}  \geq 165 \text{ g/L (female)} $
Platelets	< 100 10  /L	> 800 10  /L

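### The AST and ALT > 3 × ULN safety summary states no baseline condition, although both are muscle enzymes in this trial, so it cannot separate new elevations from persisting or improving myositis

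*SAP*

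**What the plan says.** **Safety side.** For hematology and chemistry, SAP 4.6.3.1 states that "summary tables of potentially clinically significant abnormalities will also be provided". The thresholds are in SAP 6.5 ("Potentially Clinically Significant Criteria"). AST and ALT are each potentially clinically significant when above 3 × ULN, in the same list as total bilirubin (> 2 × ULN) and alkaline phosphatase (> 3 × ULN). Neither section mentions baseline, new onset, a multiple of baseline, or a denominator. The same SAP section plans shift tables from baseline to worst post-baseline category, and for these "Clinical laboratory tests with normal ranges will be classified as low, normal, and high".

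**Disease side.** SAP 4.3.4 states: "Muscle enzymes are classified as the following 5 laboratory parameters: creatine kinase, aldolase, alanine aminotransferase, aspartate aminotransferase, and lactate dehydrogenase". For the TIS, SAP 4.2.1 (Table 3 footnotes) states: "The most abnormal muscle enzyme will be selected from the following at Baseline and followed over time". The list that follows includes ALT and AST, so either can be the enzyme component of the primary endpoint. SAP 4.3.3 also models change from baseline in each of the five enzymes by MMRM.

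**Entry.** Under Protocol 5.1, criterion 8d, one of five alternative ways to show active disease is "At least 1 muscle enzyme (CK, LDH, aldolase, AST, ALT) in the IMACS panel" at or above 2 × ULN. Criterion 7 counts an enzyme at or above 1.3 × ULN toward disease severity. The exclusion criteria in Protocol 5.2 set no upper limit for AST or ALT.

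**The concern.** An absolute cut-off is a reasonable safety screen when participants start near normal. Here the disease itself raises AST and ALT, and nothing caps them at entry. A value above 3 × ULN on treatment may therefore be a new elevation, unchanged myositis, or myositis that has improved and not yet fallen below the line. A count that pools the three does not tell a reader comparing arms what changed after dosing. The listing of AST and ALT beside bilirubin and alkaline phosphatase invites a liver reading, although the SAP does not label the table that way.

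What is at stake is the interpretation of a descriptive safety table with 24 ravulizumab and 12 placebo participants, where one or two cases alter the impression given.

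**Working it through.** The plan gives no figure to reproduce on this point. The check applies the SAP's own rules to the same AST or ALT values.

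**Inputs**
- TIS enzyme rule (SAP Table 3): percentage change = 100 × (follow-up − baseline) / range, where a decrease is improvement. Footnote d sets the "alanine aminotransferase, aspartate aminotransferase, and lactate ranges" at 3 × ULN.
- Enzyme scores (SAP Table 3): 0 up to 5% improvement, 2.5 for > 5% to 15%, 5 for > 15% to 25%, and 7.5 above 25%, which is the maximum.
- Safety flag (SAP 6.5): follow-up > 3 × ULN.
- Shift category (SAP 4.6.3.1): low, normal or high.

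**Step 1: the rules applied to single values.** Take AST or ALT as the most abnormal baseline enzyme, and take the follow-up value as the worst post-baseline value.

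| Baseline → follow-up (× ULN) | Improvement, 100 × (baseline − follow-up)/3 | TIS enzyme score | > 3 × ULN? | Shift table |
|---|---|---|---|---|
| 5.0 → 3.5 | 100 × 1.5/3 = 50% | 7.5 | yes | high to high |
| 4.0 → 3.1 | 100 × 0.9/3 = 30% | 7.5 | yes | high to high |
| 3.5 → 3.5 | 0% | 0 | yes | high to high |
| 1.5 → 10 | 100 × (−8.5)/3 = −283% | 0 | yes | high to high |
| 0.8 → 2.9 | 100 × (−2.1)/3 = −70% | 0 | no | normal to high |

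The first and fourth rows carry the point. A fall from 5.0 to 3.5 × ULN earns the full enzyme score, and a rise from 1.5 to 10 × ULN is a large new elevation. Both meet the safety criterion and both sit in the same shift cell, so neither summary separates them. This needs no assumption about how common such participants are.

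**Step 2: what the other planned displays add.**
- Change from baseline by visit and boxplots (SAP 4.6.3.1) describe the arm's distribution, not the number of participants crossing a threshold.
- The enzyme MMRMs (SAP 4.3.3) estimate mean change.
- The listings (SAP 4.6.3.1) show each participant's course but give no arm comparison.
- AE review (Protocol 8.2.6 and 10.4.1) sets aside laboratory findings associated with the underlying disease unless they are more severe than expected. This reaches the AE tables by investigator judgment and does not alter the laboratory criterion.

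None of these gives a count by arm of participants at or below 3 × ULN at baseline who later exceed it.

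**Step 3: illustration of size.** The documents give no baseline AST/ALT distribution. Assume that 10% to 30% enter above 3 × ULN and stay there:
- Ravulizumab: 24 × 0.10 = 2.4 to 24 × 0.30 = 7.2 flagged.
- Placebo: 12 × 0.10 = 1.2 to 12 × 0.30 = 3.6 flagged.

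A treatment-emergent count would record none of these participants, because all are above the threshold at baseline.

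**The case against.** The strongest reply is that the gap is read from silence. SAP 4.6.3.1 says only that the tables will be produced, and SAP Section 1 places table specifications in a separate Data Presentation Plan, which was not available. That plan may condition on baseline. This stands as a limit: the documents show that the SAP states no baseline rule, not that the programmed table will lack one. The criteria are set in the SAP, however, so the rule belongs there too.

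A second reply is that baseline context is substantial: change summaries, boxplots, flagged listings, per-enzyme MMRMs and investigator review of every laboratory report. With 36 participants, individual review is feasible, and the shift table does show normal-to-high changes. This also stands in part. The information can be recovered, but the plan does not summarize it by arm at the threshold the SAP itself chose.

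Third, criterion 8d is one of five routes, can be met by CK, LDH or aldolase alone, and uses 2 × ULN, below the flag. It does not show that many participants enter with AST or ALT above 3 × ULN. That is correct. The entry criteria allow such participants without saying how many there will be.

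A reader might go further and infer that effective treatment would clear flags from the ravulizumab arm and so conceal real hepatic cases. The documents do not support that. They give no baseline distribution, no rate at which treatment would clear elevations, and no expected hepatic signal. Protocol Table 6 lists no hepatic risk for ravulizumab, and the only adverse event of special interest is meningococcal infection.

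**Conclusion.** The point holds as a limitation of interpretation. The SAP applies an absolute > 3 × ULN criterion to two enzymes that are also disease measures, states no baseline condition, and plans no other summary by arm that isolates new crossings of the threshold. The ambiguity follows directly from SAP 4.6.3.1, SAP 6.5 and SAP Table 3.

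Its practical size is unknown. The flagged counts above rest on an assumed 10% to 30% share above 3 × ULN at entry and on those values persisting, and they serve only as illustration. The finding concerns a descriptive table in the Phase 2 part. It does not touch the primary test, alpha or sample size, and it is no evidence of a liver signal. A modest amendment is worthwhile because the data are already collected.

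**What to change.** In SAP 4.6.3.1 and 6.5, for AST and ALT:

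1. Keep the overall count of participants with a post-baseline value > 3 × ULN.
2. Add a treatment-emergent count by arm: worst post-baseline value > 3 × ULN among participants at or below 3 × ULN at baseline, with that group as the denominator.
3. Show all participants in a baseline-by-worst-post-baseline shift table in ULN multiples, for example ≤ 1, > 1 to 3, > 3 to 5, > 5 to 10 and > 10, so that rises from an already high baseline stay visible.
4. Optionally, list each emergent case with concurrent CK, GGT and total bilirubin. All three are in Protocol Table 19.

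The cost is SAP wording and one extra table, plus the optional listing. No visit, sample or clinical rule changes. The emergent count has a smaller denominator. It misses rises that start above 3 × ULN and includes small crossings such as 2.9 to 3.05 × ULN, so it should be read with the shift table. If the Data Presentation Plan already holds a baseline rule, stating that rule in the SAP would meet the treatment-emergent part.

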#### 4.6.3.2. Vital Signs

Vital signs include systolic and diastolic blood pressure (mmHg), heart rate (beats per minute), respiratory rate (breaths per minute), temperature (degrees Celsius [°C] or degrees Fahrenheit [°F]), and oxygen saturation (%).

Tabular summaries of actual and change from Baseline in each vital sign will be summarized at each scheduled visit.

A by-participant listing of vital signs will be also presented.

#### 4.6.3.3. Electrocardiograms

ECG parameters include heart rate, PR interval, QRS interval, RR interval, QT interval, QT interval, QT interval corrected using Fridericia's formula (QTcF), and interpretation.

For ECG parameters, these will be summarized using descriptive statistics of the actual values and change from Baseline by scheduled visit. In addition, the number and percentage of participants with normal, abnormal and not clinically significant, and abnormal and clinically significant will be summarized.

Shift tables from baseline to postbaseline maximum QTcF and maximum change from Baseline in QTcF will be summarized. The incidence of notable ECG changes from Baseline in maximum absolute intervals ( $\leq 450 \text{ ms}$ ,  $> 450 \text{ to} \leq 480 \text{ ms}$ ,  $> 480 \text{ to} \leq 500 \text{ ms}$ , and > 500 ms), as well as in QTcF, maximum changes from Baseline ( $\leq 30 \text{ ms}$ , > 30 to 60 ms) over all post-treatment evaluations will be summarized.

A by-participant listing of ECG data will also be provided.

## 4.6.3.4. Physical Examinations

During the study, full and abbreviated physical examinations will be conducted throughout the study. Adverse changes from Baseline in physical examinations will be classified as AEs and analyzed accordingly. Categories of physical examinations results will be summarized by treatment group.

## 4.7. Other Analyses

This study will also include analyses of PK/PD and immunogenicity of ravulizumab as described in each section.

#### 4.7.1. **PK/PD** Analyses

The PKAS and PDAS will be used for PK/PD analyses. PK concentrations recorded below LLOQ will be set to LLOQ for calculation.

Individual serum concentrations of ravulizumab will be presented in data listings and summarized separately using descriptive statistics such as (N, n, arithmetic mean, SD, CV%, median, minimum, and maximum) by sampling timepoint. Graphics of mean serum concentration-time profiles will be constructed. Graphics of serum concentration-time profiles for individual participants may also be provided.

PD analyses will be performed using the PDAS. Descriptive statistics will be presented by summarizing absolute values, changes from Baseline, and percentage changes from Baseline in free and total C5 serum concentrations over time, as appropriate. Boxplots of absolute values of free and total free C5 serum concentrations by study visit will be constructed.

Assessments of ravulizumab PK/PD relationship may be explored using data from this study or in combination with data from other studies.

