All participants completing the OLE Period (130 weeks for Part A or 74 weeks for Part B) will have an End of Study (EOS) Visit at Week 156 (Part A) or Week 124 (Part B) and a follow-up phone call 21 weeks (± 1 week) after the participant's last dose of study intervention to collect information on concomitant medications, non-pharmacologic therapies and procedures, and adverse events (AEs).

Adjustments of 'protocol allowed' DM medications (Section 6.5.1) will be permitted throughout the OLE Period.

Participants who discontinue study intervention are encouraged to complete the visits and assessments of the OLE Period (see Section 7.1).

Participants who discontinue/withdraw from the study will complete an Early Termination (ET) Visit and a follow-up phone call (see Section 7.2).

Participants from Part A (Phase 2) will not be enrolled in Part B of the study (Phase 3).

Disclosure Statement: This is a blinded, parallel group intervention study with 2 treatment arms followed by an OLE Period. Both Part A and Part B follow this design.

Number of Participants: Participants will be screened until enough participants have been enrolled to achieve an estimated total of approximately 36 participants in Part A (24 ravulizumab:12 placebo) and approximately 114 participants in Part B (76 ravulizumab: 38 placebo).

Intervention Groups and Duration: Eligible participants will be enrolled into the study and will be randomized in a 2:1 ratio (Part A) or stratified by cutaneous manifestations CDASI activity score (\leq 14 and > 14) and randomized in a 2:1 ratio (Part B) to receive intravenous (IV) ravulizumab or placebo (Section 6.3.1) within each stratum.

The study intervention dose for each participant will be based on body weight. The dosing regimen for both Parts A and B consists of a loading dose followed by maintenance doses administered every 8 weeks. The maintenance dosing will be initiated 2 weeks after the loading dose is administered.

The Randomized Controlled Period for Part A will be 26 weeks in duration. The Randomized Controlled Period for Part B will be 50 weeks in duration. Participants may continue to receive ravulizumab or for up to 130 weeks (approximately 2.5 years) (Part A) or up to 74 weeks (approximately 1.5 years) (Part B) in the OLE Period, or until ravulizumab is registered or

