| Urinalysis | X | X | X | X | X | X | | |
| FSH | X | | | | | | | Performed at Screening in selected female participants to confirm postmenopausal status. |
| Pregnancy test (WOCBP only) | X | X | X | X | X | X | X | Local urine testing will be standard for this study unless serum testing is required by local regulation or ethics committees. Testing will be done at indicated visits and when necessary at Investigator's discretion (Section 8.2.7). |

Table 1: Schedule of Activities: Screening Through End of the Randomized Controlled Period for Part A (Phase 2)

| Period/Phase | Screening | | Randomi | zed Controlle | ed Period | | UV | Notes |
|--------------|------------------|-----|---------|---------------|-----------|------|----|--|
| Study Visit | 1 | 2 | 3 | 4 | 5 | 6/ET | | Participants who discontinue/withdraw from the study |
| Study Day | D-42 to -1 | D1 | D15 | D71 | D127 | D183 | | should complete the study visit (if at the site for a scheduled visit) or return for an UV as soon as possible |
| Window (day) | | | ± 2 | ± 3 | ± 3 | ± 3 | | within a week and complete the ET Visit 8 weeks after |
| Weeks | Up to 6 weeks | | W2 | W10 | W18 | W26 | | the participant's last dose of study intervention. In addition, a follow-up phone call 21 weeks (\pm 1 week) after the participant's last dose of study intervention will be performed to collect information on concomitant medications, non-pharmacologic therapies and procedures, and AEs (see Section 7.2 for more details). |
| | | | | | | | | Participants who will not enter the OLE Period will complete the assessments for Week 26 but not receive an infusion at Week 26 (see Section 6.1.1 for more details). |
| PK/PD | | B/P | T/P | T/P | T/P | T | X | Baseline (B) and trough (T) blood samples for PK and PD will be collected predose (within 90 minutes prior to the start of infusion of study intervention). Peak (P) blood samples for PK/PD samples are to be taken within the 60 minutes following completion of study intervention infusion. B and T samples may be drawn through the venous access created for the dose infusion, prior to administration of the dose. The P samples will be drawn from the participant's opposite, non-infused arm. On Day 183 (Week 26), the T sample is considered a Randomized Controlled Period assessment and the P sample is considered an Extension Period assessment. ET or UV PK/PD sample will be collected anytime. All collection times will be recorded in eCRF. |

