- 12. Any medical condition (such as, cardiac, pulmonary, renal, oncologic, psychiatric disease, or with a diagnosis of fibromyalgia) that, in the opinion of the Investigator, might interfere with the participant's participation in the trial, poses any added risk for the participant, or confounds the assessment of the participant. This includes participants with severe arthritis with limited range of motion or severe diffuse calcinosis or other condition which will prevent quantitative muscle strength testing.
- 13. History of drug and/or alcohol abuse (according to Diagnostic and Statistical Manual of Mental Disorders [DSM] 5) within 1 year of Screening Visit that would limit participant participation in the study as determined by the Investigator.

Prior/Concomitant Therapy

- 14. Participants unwilling or unable to complete an appropriate washout period for any of the prohibited medications listed in Section 6.5.2 before the Day 1 visit.
- 15. Received ≥ 1 mg/kg/day of prednisone or equivalent within 8 weeks before randomization or is currently on a prednisone or equivalent maintenance dose that is > 20 mg/day.

16. Previously or currently treated with a complement inhibitor.

Prior/Concurrent Clinical Study Experience

17. Participation in any other investigational drug study or exposure to an investigational drug or device within 30 days of Screening or 5 half-lives of the investigational drug, whichever is greater.

Other Exclusions

- 18. Participants who begin a new muscle strengthening exercise program for myositis (eg, physical therapy) in the last 4 weeks or change their current exercise regimen up to 4 weeks before the Day 1 visit. Participants should not initiate any new exercise program or change their current exercise regimen throughout the randomized phase of the trial.
- 19. Pregnant, breastfeeding, or intending to conceive during the course of the study.
- 20. Inability or unwillingness to adhere to the protocol requirements.

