6. STUDY INTERVENTION

Study intervention is defined as any investigational intervention(s), marketed product(s), placebo, or medical device(s) intended to be administered to a study participant according to the study protocol.

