9.3. Populations for Analyses

The analysis sets are defined in Table 17. Unless otherwise specified, the same definitions will be used for the statistical analyses of Part A and Part B where applicable.

Table 17: Study ALXN1210-DM-310 Analysis Populations

| Population | Description |
|------------------------|---|
| Randomized Set | All randomized participants grouped by randomized treatment group (for reporting disposition, demographics, baseline characteristics and efficacy). |
| PK Analysis Set (PKAS) | All participants who receive at least 1 dose of study intervention and have at least 1 post-dose PK sample |
| PD Analysis Set (PDAS) | All participants who receive at least 1 dose of study intervention and who have evaluable free or total C5 data |

| Population | Description | |
|---|---|--|
| Per Protocol Set (PPS) (applicable for Part B only) | All randomized participants without any major protocol deviations ^a that could impact the interpretation of efficacy. The PPS will be used for supplemental analyses of the primary and secondary efficacy endpoints. | |
| Safety Set (SS) | All participants who receive at least 1 dose of study intervention. Participants will be analyzed according to the study intervention they actually received. The SS will be used for the analysis of safety data. | |
| OLE Set | All randomized participants who received at least 1 dose of ravulizumab starting from Week 26 (Part A and Part B) onward. | |
| Immunogenicity Analysis Set (IAS) | All participants who receive at least 1 dose of study intervention and have at least one reportable result in the ADA assay. Participants will be analyzed according to the study intervention they actually received | |

Table 17: Study ALXN1210-DM-310 Analysis Populations

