## 4. STATISTICAL ANALYSES

#### 4.1. General Considerations

All data collected in this study will be presented separately by treatment arm and period (RCP, OLE) using summary tables, figures, and data listings. All analyses will be performed using Statistical Analysis Software® (SAS®) version 9.4 or higher (SAS Institute Inc., Cary, NC, USA) or other validated statistical software.

Summaries of study and participant characteristics (e.g., disposition, baseline characteristics and demographics, medical history, and protocol deviations, etc.) are described in Section 6.2.

All efficacy and safety analyses will be summarized for the RCP (up to Week 26) and the OLE Period. There may be additional summaries across the entire study period (RCP + OLE). The primary comparison will be ravulizumab treatment group versus the placebo treatment group during the RCP.

During the OLE Period, the participants who were randomized to placebo but later received ravulizumab will have additional variables created to reflect the data collected relative to the first dose of ravulizumab. At a minimum, all listings will include 2 sets of definitions for the following variables:

- Baseline value: Relative to the first randomized dose of placebo and relative to the first dose of ravulizumab in OLE.
- Study day: Relative to the first randomized dose of placebo and relative to the first dose of ravulizumab.
- Visit: Based on the actual study visit and visits re-aligned relative to the first dose of ravulizumab.

The descriptive analyses and presentations will be based on the types of variables being tested.

- 1. Overall summary of descriptive statistics for continuous variables will include but not limited to, number of observations, mean, standard deviation, median, minimum, and maximum, interquartile range, first quartile, and third quartile values. Minimum and maximum values will be reported to the same precision as the database.
- 2. Overall summary of descriptive statistics for categorical variables will include frequency counts and percentage of participants.

Formal statistical testing will be performed for the primary efficacy endpoint in the double-blind period. Testing will be conducted at the nominal 2-sided p-value of 0.20 level of significance.

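### SAP 4.7.1 sets PK values below LLOQ to LLOQ even before any ravulizumab is given, so pre-dose and placebo summaries show LLOQ where zero is expected

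*SAP*

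**What the plan says.** The rule is one sentence in SAP section 4.7.1: "PK concentrations recorded below LLOQ will be set to LLOQ for calculation". The same section fixes the populations: "The PKAS and PDAS will be used for PK/PD analyses". It asks for mean, SD, CV%, median, minimum and maximum at each sampling time, for mean concentration-time graphs, and separately for listings of individual concentrations.

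Protocol section 9.3 (Table 17) defines the PK set as "All participants who receive at least 1 dose of study intervention and have at least 1 post-dose PK sample"; SAP section 3 matches. Protocol section 6 makes clear that placebo counts: "Study intervention is defined as any investigational intervention(s), marketed product(s), placebo, or medical device(s) intended to be administered to a study participant".

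On sampling, the Part A Schedule of Activities (Protocol 1.3, Table 1) says "Baseline (B) and trough (T) blood samples for PK and PD will be collected predose", so everyone has a PK sample before the first infusion. Exclusion criterion 16 (Protocol 5.2) bars anyone "Previously or currently treated with a complement inhibitor".

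On layout, SAP section 4.1 says "All data collected in this study will be presented separately by treatment arm and period (RCP, OLE"). Protocol section 9.4.3.1 gives no rule for values below LLOQ, so the SAP sentence is the only one that applies.

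**The concern.** Ravulizumab is an exogenous antibody. Before the first dose of it, the expected serum concentration is zero, not an unknown amount between zero and the LLOQ. Replacing such a value by the LLOQ puts in a number that is known to be too high.

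Serum ravulizumab concentration is a listed endpoint in both documents. A table built by the stated rule would give undosed participants a positive concentration with no variability, and the mean profile would start above zero. Those figures come from the imputation and not from the assay. SAP 4.7.1 does not ask for the number of values below LLOQ, so a reader of the summary table could not tell imputed from measured values.

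**Working it through.** There is no stated figure to reproduce. The check is whether the consequence follows from the text, and how many planned samples it touches.

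**Does it follow?**

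1. The substitution rule has no exception for pre-dose or placebo samples, in section 4.7.1 or elsewhere in either document.
2. Placebo is study intervention, so a placebo participant with one infusion and one post-dose PK sample is in the PK set.
3. Prior complement-inhibitor treatment is excluded, so no ravulizumab is expected in the Day 1 pre-dose sample of either arm.
4. Placebo participants receive their first ravulizumab at Week 26. The Day 183 trough is drawn before that infusion and is counted in the randomized period, so all their samples in that period precede any ravulizumab.
5. These values therefore enter the summaries as LLOQ whenever they are recorded below LLOQ.

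**What the summary shows.** Write L for the LLOQ, and take 12 placebo participants all below LLOQ at one timepoint:

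| Value substituted | Mean | Median | Min | Max | SD | CV |
|---|---|---|---|---|---|---|
| L (SAP rule) | L | L | L | L | 0 | 0% |
| 0 | 0 | 0 | 0 | 0 | 0 | undefined |

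The first row also describes the 24 ravulizumab-arm values at Day 1 pre-dose.

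**How many samples?** Inputs: 24 ravulizumab and 12 placebo participants (Protocol 1.1), and the PK row of Table 1.

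- Samples per participant: Day 1, 2 (baseline and peak); Days 15, 71 and 127, 2 each (trough and peak); Day 183, 1 (trough). Total 2 + 3 × 2 + 1 = 9.
- Ravulizumab arm: 24 × 9 = 216 planned samples, of which 24 × 1 = 24 precede the first dose. 24/216 = 11.1%, all at one timepoint.
- Placebo arm: 12 × 9 = 108 planned samples, all before any ravulizumab.

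**Size per value.** The true value is 0 and the substituted value is L, so the error is L. Any other value below LLOQ lies between 0 and L, so its error is at most L.

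**The case against.** Much of the case for leaving the sentence alone is sound.

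- **Listings.** A reader might infer that undosed participants will be reported individually as having measurable drug. The documents do not support that. The rule applies to calculation, and nothing says the listings carry the substituted value. The point is confined to calculated summaries and mean plots.
- **Ravulizumab means.** A reader might infer that placebo values dilute the active-arm means. Presentation by arm rules this out. SAP 4.7.1 asks for change from baseline only for free and total C5, so the imputed PK baseline is not carried into any later PK summary.
- **Misdosing.** It is tempting to say the rule hides a placebo participant given ravulizumab in error. It does not. A quantified value above LLOQ stands out as a raised maximum and a non-zero SD, and a value below LLOQ is equally unquantified whether replaced by 0 or by LLOQ.
- **Share of samples.** Adding the two counts gives 108 + 24 = 132 of 324 planned samples (41%). That counts samples, not error, and 108 of them are placebo. It is not a measure of impact on the description of ravulizumab exposure.
- **Convention.** Substituting LLOQ is prespecified and matches the rule for safety laboratory values in SAP 4.6.3.1. For post-dose values it is one convention among several, and the documents give no reason to prefer another, such as LLOQ/2.
- **Unseen layout.** SAP section 1 leaves table, figure and listing specifications to a separate Data Presentation Plan, which might omit placebo columns or add counts below LLOQ.

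What remains is that the SAP's calculation rule gives a wrong value for samples with no drug. The laboratory convention suits analytes naturally present in the body, not an antibody that has not been given. The layout plan might limit where the value appears, but the SAP sentence still sets it.

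**Conclusion.** The point stands as a minor error in a stated rule. Followed literally, the Day 1 pre-dose summaries in both arms, and every placebo summary and mean plot in the randomized period, show LLOQ with SD 0 where zero is expected.

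The size is at most one LLOQ per value and cannot be given in concentration units. In the ravulizumab arm the effect is certain only at the pre-dose timepoint. Post-dose samples below LLOQ could occur, but the documents give no expected number, and substituting LLOQ there is a matter of convention. Post-dose levels, efficacy, safety and PD results are not materially affected.

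The conclusion assumes that pre-ravulizumab samples do assay below LLOQ and that the exclusion of earlier complement inhibitors is respected. The counts assume full recruitment and attendance.

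**What to change.** Amend the sentence in SAP 4.7.1 along these lines: *For calculation, concentrations below LLOQ in samples taken before a participant's first dose of ravulizumab, including all placebo samples in the Randomized Controlled Period, are set to 0; other concentrations below LLOQ are set to LLOQ. The number of values below LLOQ is reported at each timepoint. Summaries and mean plots of ravulizumab concentration in the Randomized Controlled Period use the ravulizumab arm; placebo concentrations are listed.* Where the mean is 0, show CV% as not calculable.

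Moving the PK summaries to the All Ravulizumab-Treated Set in SAP section 3 would not be enough by itself. That set includes placebo participants who switch in the extension, and it leaves the pre-dose value at LLOQ.

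The cost is a short SAP edit and a small programming change. No extra data, sampling or design change is needed.
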